#### 4.3.2 Blinding

No blinding will be performed in this study.

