## 8.1.4 Evaluation of causal relation with the study drug

Causal relation of AEs with each study drug shall be evaluated for the following 2 levels, and accordingly recorded in EDC.

- Related: There is a possible reasonable causality between the study treatment and AE.
- Unrelated: There is no reasonable causality between the study treatment and AE.

Causality between the study treatment and AE should be evaluated in consideration of;

- Temporal relationship between the timing of AE and the start of study treatment;
- Clinical course of AE, especially the effect of discontinuation and/or resumption of study treatment if applicable;
- Whether the AE is known for the study drug or drugs of the same class;
- The presence/absence of risk factor that may increase the incidence of AE in subjects with the underlying disease; and
- The presence/absence of confounding factors related to AE but unrelated to the study drug.

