## 8.2 **Procedures for collection, documentation, and reporting of SAEs**

Upon detection of an SAE, the principal investigator shall report all SAEs regardless of the causality with the study drug to the study secretariat (SAE Report Center) as promptly as possible (within 1 business day in principle) using the SAE report form (Attachment 1). The principal investigator shall also report the information to Hospital Director (also to the Ethical Review Board in South Korea and Taiwan) if he/she judges that the SAE is causally "related" to the study drug. When sub-investigators, etc. other than the principal investigator detect a suspected SAE, they shall report it to the principal investigator and Eisai Co., Ltd. within 2 business days after receiving the information. The Lead Principal Investigator reports a drug-related SAE to the Certified Review Board within the period specified by the Clinical Trials Act and also should report it to the principal investigators of the other study sites. In Japan, the principal investigators who receive the report shall report the event to Hospital Director of the study site to which they belong.

All SAEs that occur on or before the final study-related visit should be collected regardless of the causality with the study treatment. All SAEs must be followed up until they are resolved,

or their symptoms stabilize if not expected to be resolved. Any SAE after study completion, for which a causality with the study drug (or protocol-specified procedures) cannot be ruled out as judged by the principal investigator or sub-investigator, must be reported to the study secretariat regardless of the time from study completion.

It is important to complete the initial SAE report Form as detailed as possible including the evaluation of causality with the study treatment as determined by the principal investigator or sub-investigator.

Any follow-up information received on SAEs should be forwarded by the principal investigator to the study secretariat within 1 business day of its receipt. If the follow-up information changes the investigator's assessment of causality, this should also be noted on the follow-up SAE report form.

Preliminary SAE reports should be followed as soon as possible by detailed descriptions including copies of hospital case reports, autopsy reports, and other documents requested by the study secretariat.

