## 9.2.3.1 Adverse events (AEs)

AEs recorded in EDC will be reinterpreted with ICH Medical Dictionary for Regulatory Activities (MedDRA). AEs recorded in EDC will be reinterpreted to the closest MedDRA lowest level terms (LLT) (Ver. 19.0 or later version). Preferred term (PT) and system organ class (SOC) will also be entered in the database. Treatment-emergent adverse events (TEAE) means AEs not confirmed before the study treatment (MTX) and emerges for the first time after the start of study treatment. TEAE also includes:

- Events confirmed before the study treatment which disappears immediately before the start of study treatment, but reemerges during the study treatment; and
- Events confirmed before the study treatment, which becomes severer during the study treatment compared to the level of severity before the start of study treatment.

TEAE will be used for the analysis of AEs. The number (proportion) of subjects with TEAE in each ARM will be tabulated in SOC and PT. Two or more AEs with the same MedDRA term may be reported in a single subject; in such case, the AEs will be interpreted and counted as 1 subject pertinent to the analysis, and also the AE with the highest severity will be counted in for the analysis on the number (proportion) of subjects with the TEAE. Furthermore, the number (proportion) of subjects with TEAE will be tabulated by the presence/absence of causality.

In addition, TEAE for which causality with the study treatment cannot be ruled out (ADR) will be tabulated in terms of SOC and PT, and the AEs with the highest severity will be counted in for the analysis on the number (proportion) of subjects.

The incidence of TEAE that occur from Week 24 to 48 will be compared between ARM-2 and ARM-3 using a Fisher's exact test or other relevant method.

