7.1. Analysis Plan of Adverse Events (AEs)

7.1.1. Onset of AEs

Number and proportion of subjects with AEs among all the subjects enrolled in this study (i.e., subjects randomized to ARM-1, 2 or 3, and those who discontinued the study before Week 24) will be tabulated by System Organ Class (SOC) and Preferred Term (PT) (see the Protocol for the details of categories and summarization). Two or more AEs with the same MedDRA term may be reported in a single subject; in such case, the AEs will be interpreted and counted as 1 subject to the analysis. Furthermore, the number and proportion of subjects with AEs by highest severity will be tabulated by presence/absence of causality with the study treatment for each ARM.

Furthermore, the number and proportion of subjects with AEs will be tabulated for each treatment period (Week 0 to Week 24, and Week 24 to Week 48) by SOC and PT. Moreover, the number and proportion of subjects with AEs at Week 24 onward will be tabulated for each ARM (ARM-1, 2, and 3) by SOC and PT.

7.1.2. Incidences of AEs for which causality with the study treatment cannot be ruled out Treatment-emergent adverse events (TEAE) for which causality with the study treatment cannot be ruled out will be tabulated at each assessment timepoint for each ARM (ARM-1, 2, and 3) by SOC and PT. In addition, the number and proportion of subjects with AEs by highest severity will be tabulated for each ARM. The incidences of TEAEs for which

causality with the study treatment cannot be ruled out that occur from Week 24 to 48 will be compared between ARM-2 and ARM-3 using a Fisher's exact test.

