9.1. Revision from Protocol

Date	Name	Addresses for distribution	Revised contents
Not applicable			

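### The SAP tests only treatment-related TEAEs between ARM-2 and ARM-3, where the protocol tests all TEAEs; the change is undeclared and ties the only AE-incidence test to unblinded attribution

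*SAP*

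**What the plan says.** Protocol 9.2.3.1 makes TEAEs the basis of the AE analysis and gives the causally related subset its own name: "TEAE for which causality with the study treatment cannot be ruled out (ADR) will be tabulated in terms of SOC and PT". No test is attached to that subset. The section ends with the between-arm comparison: "The incidence of TEAE that occur from Week 24 to 48 will be compared between ARM-2 and ARM-3", by Fisher's exact test or another suitable method. That sentence carries no causality restriction.

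SAP 7.1.1 handles AEs of any cause descriptively: "the number and proportion of subjects with AEs at Week 24 onward will be tabulated for each ARM". The test appears in SAP 7.1.2 and covers only the events whose "causality with the study treatment cannot be ruled out that occur from Week 24 to 48 will be compared between ARM-2 and ARM-3"; the method is Fisher's exact test. SAP 9.1, the table for departures from the protocol, reads "Not applicable".

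On how causality is judged, Protocol 4.3.2 states: "No blinding will be performed in this study". Protocol 8.1.4 sets a related/unrelated scale: "Causal relation of AEs with each study drug shall be evaluated for the following 2 levels". Protocol 8.2, on SAE reports, refers to "the evaluation of causality with the study treatment as determined by the principal investigator or sub-investigator".

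**The concern.** The tested set and the tabulated set have changed places between the two documents, and nothing records that this was intended.

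The difference matters in this design. Protocol 3.3 gives fewer dose-dependent MTX reactions as the expected gain from the lower dose, so the AE comparison bears directly on the case for ARM-3. Whether an event counts as related is a judgement. Protocol 8.1.4 asks the rater to consider whether the event is already known for the drug. A rater who knows that a patient was cut to 6 to 8 mg/week may be less ready to attribute an event to MTX than one whose patient stayed on 10 to 25 mg/week. That would lower the related-event count in ARM-3 even if the events were the same. The protocol's all-TEAE test does not pass through this judgement; the SAP's test does. With two conflicting documents and no declared change, it is also unclear which comparison should be treated as pre-specified.

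**Working it through.** **Comparison of the texts**

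| Item | Protocol 9.2.3.1 | SAP 7.1.1 and 7.1.2 |
|---|---|---|
| All TEAEs/AEs from Week 24 | tested, ARM-2 vs ARM-3 | tabulated by arm |
| TEAEs with causality not excluded | tabulated | tested, Fisher's exact |
| Declared change | – | none in SAP 9.1; not mentioned in the SAP 9.2 log |

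Three readings that might reconcile the documents fail:

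- The protocol's comparison sentence cannot mean related events only, because the preceding paragraph has a separate label (ADR) for them.
- SAP 7.1.1 refers back to the protocol for how events are categorised and summarised. That does not bring in the between-arm test.
- The protocol's allowance for another relevant method permits a different test, not a different set of events.

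The tests in SAP 7.2 concern laboratory values, vital signs and body weight, so SAP 7.1.2 holds the only test of AE incidence.

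**Size of the possible effect (illustration)**

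The plan states no figure to reproduce. From the documents: 110 per arm (Protocol 9.4.1) and two-sided 5% (Protocol 9.3; SAP 2.6). Everything else is assumed: true TEAE incidence *I*, equal in both arms, and attribution probability *a* by arm.

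With one event per affected subject, the related-event rate is *I* × *a*. For *I* = 60%, attribution of 50% vs 40% gives 0.60 × 0.50 = 0.30 vs 0.60 × 0.40 = 0.24. The rejection probability is the sum, over all pairs of counts, of the two binomial probabilities for every table with Fisher p ≤ 0.05:

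| Attribution, ARM-2 vs ARM-3 | *I* = 40% | *I* = 60% | *I* = 80% |
|---|---|---|---|
| 50% vs 45% | 4.7% | 5.8% | 7.0% |
| 50% vs 40% | 8.9% | 13.5% | 19.4% |
| 50% vs 35% | 17.2% | 28.1% | 41.6% |
| 50% vs 30% | 30.3% | 49.1% | 67.7% |

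With equal attribution of 50% at *I* = 60%, the related-only test rejects in 3.5% of trials (Fisher's test is conservative). The all-TEAE test at 60% vs 60% rejects in 3.4%, whatever the attribution.

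**What shrinks the effect** (*I* = 60%, 50% vs 40%)

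- With *k* independently attributed events per affected subject, the rate is 0.6 × [1 − (1 − *a*)^*k*]. Rejection is 13.2% for *k* = 2, 10.2% for *k* = 3 and 5.1% for *k* = 5.
- Both arms receive ADA. If half of affected subjects in each arm have an event attributed to ADA, the rate with one event is 0.6 × (0.5 + 0.5*a*) = 0.45 vs 0.42, and rejection is 5.4%.
- Combining the two, the rate is 0.6 × {0.5 + 0.5 × [1 − (1 − *a*)^*k*]}. Rejection is 5.9%, 5.1% and 3.8% for *k* = 2, 3 and 5.

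**Limits of the all-TEAE test**

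- Recording is also open-label. A recording gap of 60% vs 54% gives rejection in 11.4%.
- It can dilute a real effect. Suppose MTX-related events truly fall from 30% to 15%. The related-event test detects this 71.7% of the time. If 30% of subjects independently have other events, the all-TEAE rates are 1 − 0.7 × 0.7 = 0.51 and 1 − 0.85 × 0.7 = 0.405, and power is 29.6%.

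**The case against.** The strongest reply is that little is lost. This is one unpowered secondary safety p-value with no multiplicity control, and the primary non-inferiority conclusion does not depend on it. All AEs from Week 24 are still tabulated by arm. Hepatic and haematological effects, two of the dose-dependent MTX toxicities named in Protocol 2.2.1, are compared in SAP 7.2 without a causality filter. A related-event comparison suits the trial's purpose and can be the more powerful one. The larger rejection rates above need a wide attribution gap and a single event per subject. The evidence on who rates causality is also incomplete: Protocol 8.2 speaks of the SAE form, and Protocol 8.1.4 names no rater.

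Much of this stands as a limit on weight. It does not remove the point:

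- A test computed later from the tables would be post hoc, and the SAP does not say that the table will carry an any-AE row.
- The laboratory comparisons leave gastrointestinal symptoms, also named in Protocol 2.2.1, without a test that is free of attribution.
- Protocol 8.1.4 has causality recorded in the EDC, and Protocol 13.1 has the investigator enter EDC data. Site attribution of ordinary AEs is therefore the natural reading, though an inference.
- The merits of the related-event test justify adding it, not substituting it without a record.

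**Conclusion.** The point holds. Following the SAP drops the protocol's comparison of all Week 24 to 48 TEAEs and replaces it, undeclared, with one filtered by causality judged in an open-label trial. The textual conflict is certain and needs no assumption. The reach of attribution bias rests on two things: that site staff who know the arm rate causality, and that their ratings differ by arm. The documents support the first and cannot settle the second. Its size is therefore unknown. In the illustrations, a gap of 50% vs 40% at 60% incidence gives anything from 3.8% to 13.5% false-positive findings, depending on events per subject and shared ADA attribution. This should be corrected because reduced toxicity is the argument for the lower dose. It does not threaten the primary analysis.

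**What to change.** In SAP 7.1, restore the protocol's comparison and keep the other, for example:

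> The proportion of subjects with any TEAE starting between Week 24 and Week 48 will be tested between ARM-2 and ARM-3 with Fisher's exact test, and the risk difference given with its 95% CI. A supportive analysis repeats this for TEAEs rated as possibly caused by study treatment.

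Ranking the related-event test as supportive follows from the protocol, which tests only the full TEAE set. The risk difference with CI goes beyond the protocol, but it is more informative than a p-value alone. In SAP 9.1, record the related-event test and the risk difference as additions to Protocol 9.2.3.1. Beside the results, state that the all-TEAE test removes attribution bias but not open-label recording bias, and may dilute an MTX-specific effect.

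Cost: two sentences in SAP 7.1, one entry in SAP 9.1 and one extra table. No new data are needed.

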7.2. Analysis Plan of Clinical Laboratory Values and Vital Signs

For continuous variables, descriptive statistics of measurements at each assessment timepoint and their changes from baseline will be calculated for each ARM (ARM-1, 2, and 3). Furthermore, analysis of covariance (ANCOVA) adjusted by country will be performed to make a comparison between ARM-2 and ARM-3, and calculate the estimate of difference between the treatment arms and its two-tailed 95% confidence interval. In addition, descriptive statistics will be calculated, being stratified by country.

As an order categorical variable, clinical laboratory values will be categorized to Lower than the reference (L), Within the reference (N), and Higher than the reference (H), and then the number and proportion of subjects by L, N, and H will be presented in a shift table (baseline vs. each visit during treatment) for each ARM (ARM-1, 2, and 3). In addition, the maximum and minimum values after the start of treatment will be presented in a shift table for comparison with baseline. Furthermore, Wilcoxon rank sum test will be performed to make a comparison between ARM-2 and ARM-3.

Descriptive statistics of vital signs (diastolic blood pressure, systolic blood pressure, pulse rate, body temperature) and body weight at each assessment timepoint and their changes from baseline will be computed for each ARM (ARM-1, 2, and 3). Furthermore, analysis of covariance (ANCOVA) adjusted by country will be performed to make a comparison between ARM-2 and ARM-3, and calculate the estimate of difference between the treatment arms and its two-tailed 95% confidence interval.

8. Analysis Plan of Exploratory Endpoints

8.1. Erythrocyte MTX-PG Concentration at Weeks 0, 4, 8, 12, 24, 36, and 48 Descriptive statistics for erythrocyte MTX-PG concentrations as well as change from baseline and change rate from baseline will be calculated by country. In addition, descriptive statistics for Week 24 onward will be calculated at each assessment timepoint for each ARM (ARM-1, 2, and 3).

Pearson's product-moment correlation coefficient, Spearman's rank correlation coefficient, and their 95% confidence interval will be calculated at each assessment timepoint to evaluate the correlation of exposure to MTX, SDAI, mTSS, and ACR-N to erythrocyte MTX-PG concentration. Furthermore, cutoff values for AST increased, ALT increased, and WBC decreased, and their differences among the participating countries will be discussed.

8.2. Blood Cytokine (IL-6, VEGF) at Weeks 0, 24, and 48

Descriptive statistics for blood cytokine (IL-6, VEGF) levels as well as change from baseline and change rate from baseline will be calculated at each assessment timepoint for each ARM (ARM-1, 2, and 3).

8.3. Plasma Micro RNA at Week 24

Pearson's product-moment correlation coefficient, Spearman's rank correlation coefficient, and their 95% confidence interval will be calculated to evaluate the correlation of SDAI and ACR-N to plasma micro RNA levels at Week 24.

8.4. Serum Anti-adalimumab Antibody at Weeks 24 and 48

For serum anti-adalimumab antibody, the frequency of and the proportion of subjects with the antibody expression will be calculated at each assessment timepoint for each ARM (ARM-1, 2, and 3).

9. Revision History

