## 7.4.1 Evaluation of AEs

Principal investigator/sub-investigator shall monitor for possible occurrence of AEs throughout the course of this study, and record in EDC all AEs that occur in the study. The following ADRs are known for the study drug; for which, treatment should be given according to respective symptoms. Also, any event suspected to be related to the study drug or for which treatment discontinuation is expected to improve conditions or prevent progression should be managed with dose reduction or treatment discontinuation. <MTX>

- 1) Shock, anaphylaxis
- 2) Bone marrow depression

- 3) Infection
- 4) Tuberculosis
- 5) Hepatitis fulminant/hepatic failure
- 6) Acute renal failure, tubular necrosis, severe nephropathy
- 7) Interstitial pneumonia/pulmonary fibrosis/pleural effusion
- 8) Toxic epidermal necrolysis (TEN), oculomucocutaneous syndrome (Stevens-Johnson syndrome)
- 9) Enterocolitis haemorrhagic, necrotising enterocolitis
- 10) Pancreatitis
- 11) Osteoporosis
- 12) Encephalopathy (including leukoencephalopathy)
- 13) Lymphoproliferative disorder

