2.3. Handling of Study Data

- · Fixed data after the completion of follow-up will be used for statistical analyses.
- For subjects who were enrolled more than once, statistical analyses will be conducted by removing the data that became unnecessary.
- Data handling meeting will be held prior to the database lock to discuss and determine how to handle individual data after removing the information on which treatment arm each subject was randomized to.
- For clinical laboratory values that exceed or fall below detection limits, detection limits will be substituted for actual values.
- As a rule, baseline is defined as Week 0. If the value at Week 0 is missing or not measured, the time of screening is regarded as baseline.
- · Change and percentage change are defined as follows:

Change = measured value after intervention – measured value at baseline Percentage change = (change/measured value at baseline) x 100 (%)

- 2.4. Handling of Missing Values
 - Subjects with missing data at an assessment time point of SDAI remission, ACR20, ACR50, and ACR70 response, HAQ remission, and structural remission due to study discontinuation or other relevant reasons will be considered as a "non-responder" at the time point of missing data.
 - Subjects with missing data at an assessment time point of CDAI, DAS28-ESR, DAS28-CRP remission due to study discontinuation or other relevant reasons will be considered as a "non-responder" at the time point of missing data.
 - Any missing data on SDAI, CDAI, DAS28-ESR, and DAS28-CRP will be considered as missing at the time point of missing data.

If there is a missing data on the assessment of SDAI, CDAI, DAS28-ESR, DAS28-CRP, and mTSS, the sensitivity analysis of GEE or MMRM method will be performed. If the result does not converge, a missing data will be imputed with the last observation carried forward (LOCF). In addition, for the sensitivity analysis of primary endpoint, a missing data on the final scheduled visit will be imputed with data on End of Study.

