2.7. Descriptive Statistics

Descriptive statistics (number of subjects, mean, standard deviation, minimum, median, and maximum as continuous variables, and number and proportion [%] of subjects as nominal variables) will be computed.

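### No planned laboratory table counts, by randomised arm, subjects with marked liver or blood abnormalities after the MTX dose changes at Week 24

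*SAP*

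**What the plan says.** For laboratory values, SAP 7.2 plans:

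- Summaries by visit and arm (SAP 2.7: "number of subjects, mean, standard deviation, minimum, median, and maximum as continuous variables"), with "analysis of covariance (ANCOVA) adjusted by country will be performed to make a comparison between ARM-2 and ARM-3".
- Three categories: "clinical laboratory values will be categorized to Lower than the reference (L), Within the reference (N), and Higher than the reference (H". Subjects are counted in these categories at each visit against baseline, by arm.
- One worst-value output: "the maximum and minimum values after the start of treatment will be presented in a shift table for comparison with baseline".
- A Wilcoxon rank sum test of ARM-2 against ARM-3, without saying which of these tables it applies to.

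SAP 2.3 adds: "As a rule, baseline is defined as Week 0". Protocol 9.2.3.2 has the same categories and the same worst-value table, and sets no threshold.

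Other sections bear on the same question:

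- **AE tests.** Protocol 9.2.3.1: "The incidence of TEAE that occur from Week 24 to 48 will be compared between ARM-2 and ARM-3". SAP 7.1.2 plans a Fisher test of possibly treatment-related events only, those whose "causality with the study treatment cannot be ruled out that occur from Week 24 to 48 will be compared between ARM-2 and ARM-3".
- **AE tables.** SAP 7.1.1 tabulates AEs from Week 24 by arm, SOC and PT.
- **When a laboratory change is an AE.** Protocol 8.1.1 makes it one if it leads to stopping treatment, needs intervention, or is judged to be one.
- **Management.** Under Protocol 7.4.1, suspected drug reactions "should be managed with dose reduction or treatment discontinuation".
- **Discontinuations.** SAP 4.2 summarises them with reasons, by arm, from Week 24.
- **Cutoffs.** SAP 8.1 mentions AST, ALT and WBC cutoffs in the MTX-PG section. It gives no values and looks at differences between countries, not arms.

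**The concern.** Protocol 2.2.1 names liver and marrow harm among the MTX reactions that rise with dose, and Protocol 3.3 gives fewer such reactions as the purpose of the lower dose. The primary analysis accepts a loss of up to 15 points in remission, and lower toxicity is what would be weighed against that loss. A reader choosing between doses will ask how many subjects per arm had, say, ALT above 3 x ULN or a graded cytopenia once the doses differed.

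SAP 7.2 does not answer this, for two reasons. The three categories discard degree. The one table built on each subject's worst value includes the 24 weeks in which both future arms shared the same MTX escalation. At stake is how clearly the safety result can be read, not the non-inferiority conclusion.

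**Working it through.** The plan states no figure on this point, so there is none to reproduce. The first check is of the text; the second is an illustration on assumed rates.

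**1. Window of the worst-value table.** Protocol 6.1 starts MTX after the Week 0 assessments, and Protocol 9.2.3.1 identifies study treatment as MTX. SAP 2.3 sets baseline at Week 0. Protocol 4.3.1 randomises after the Week 24 assessments. The table therefore covers Weeks 4, 8, 12, 24, 36 and 48, and only the last two follow randomisation (Protocol 7.5). The SAP sentence does not name Week 0; this is the natural reading of these sections together.

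**2. Illustration.** All of these inputs are assumptions:

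- Background ALT/ULN is lognormal, with median 0.7, log-SD 0.5 and correlation 0.6 between visits.
- A share x of subjects (8% in ARM-2, 1% in ARM-3) is at 3 to 10 x ULN at both Weeks 36 and 48.
- A share y = 5% of both arms has a marked rise at one of Weeks 4, 8 or 12.
- The three sources are independent.

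Let b be the chance that background alone crosses the cut at least once in the window. At one visit, b = 1 − Φ(ln(cut/0.7)/0.5). This gives 1 − Φ(0.713) = 23.8% for a cut of 1, and 1 − Φ(2.911) = 0.18% for a cut of 3. Integrating over the shared component gives, for a cut of 1, 35.0% over two visits and 53.8% over six; for a cut of 3, 0.34% and 0.86%.

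Proportion = 1 − (1 − b)(1 − x)(1 − y), with y = 0 for windows after Week 24. Difference = 0.07 × (1 − b)(1 − y).

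| Output | ARM-2 | ARM-3 | Difference (points) |
|---|---|---|---|
| Worst value High, Weeks 4–48 (planned) | 59.6% | 56.5% | 0.07 × 0.462 × 0.95 = 3.1 |
| High at Week 48 (planned, by visit) | 29.9% | 24.5% | 0.07 × 0.762 = 5.3 |
| Worst value High, Weeks 36–48 (window changed only) | 40.2% | 35.6% | 0.07 × 0.650 = 4.6 |
| >3 x ULN, Weeks 4–48 (threshold changed only) | 13.4% | 6.8% | 0.07 × 0.991 × 0.95 = 6.6 |
| >3 x ULN, Weeks 36–48 (both changed) | 8.3% | 1.3% | 0.07 × 0.997 = 7.0 |

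On the difference scale, the threshold does most of the work: 3.1 to 6.6 points, against 3.1 to 4.6 for the window alone. On the ratio scale the window also matters: 13.4/6.8 = 2.0 against 8.3/1.3 = 6.4.

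Sensitivity of the planned worst-value table: with y = 0 it shows 57.5% v 54.3%, and with y = 10% it shows 61.7% v 58.8%. With a lower background (median 0.5, log-SD 0.45; b = 19.9% over six visits, 6.2% at one) the difference is 0.07 × 0.801 × 0.95 = 5.3 points. The Week 48 table then gives 0.07 × 0.938 = 6.6.

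**3. What the planned summaries can separate.** The background mean is 0.7 × exp(0.125) = 0.793, and marked rises average 6.5. The ARM-3 mean is 0.99 × 0.793 + 0.01 × 6.5 = 0.85. ARM-2 can reach 1.25 in two ways:

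- Through an 8% tail: 0.92 × 0.793 + 0.08 × 6.5.
- Through a general 1.51-fold rise with a 1% tail: 0.99 × 0.793 × 1.51 + 0.065.

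The tail gives High 29.9%, median 0.74, SD 1.70. The general rise gives 55.0%, 1.06, 0.85. The planned outputs tell these apart. They do not report the count above 3 x ULN, which is 8.2% v 2.8%, or about 9 v 3 of 110.

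**4. Precision of the proposed count**, at the planned 110 per arm with an assumed 66/22/22 country split:

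- 9 v 1 events (6, 2, 1 v 1, 0, 0): 8.2% − 0.9% = 7.3 points; Mantel-Haenszel 95% CI (Sato variance) 1.9 to 12.7, Newcombe 1.7 to 14.0.
- 5 v 1 events (3, 1, 1 v 1, 0, 0): 3.6 points; Mantel-Haenszel 95% CI −0.6 to 7.9.

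**The case against.** The strongest reply is that the plan already has laboratory counts by arm after randomisation. The shift tables at Weeks 36 and 48 use post-randomisation values only, and those are the only two scheduled laboratory visits after Week 24. In the illustration, the Week 48 table recovers 5.3 of the assumed 7 points. Marked cases should also surface elsewhere: Protocol 8.1.1 and 7.4.1 send many into the AE tables, Protocol 5.3 withdraws subjects who cannot keep their assigned dose, and SAP 4.2 lists those withdrawals with reasons. That stands as partial cover. It does not supply a count above a set level. AE entry rests on judgement in an open-label trial (Protocol 4.3.2). Severity is graded by daily activities (Protocol 8.1.3), so a symptom-free ALT of 8 x ULN can be recorded as mild.

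A second reply is that rises persisting at both visits fit poorly with the instruction to reduce or stop treatment, and that 8.3% v 1.3% largely restates the 8% v 1% input. Both are fair. The figures show what each table would display under one assumption; they do not predict the trial's result.

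A third reply is that the count brings no dependable power. That is also right. In 2,000 simulated trials of 8% v 1%, ANCOVA on raw Week 48 values had 67% power, against 59% (Fisher) to 72% (Mantel-Haenszel) for the count.

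A reader might infer three stronger things that the documents do not support:

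- **That liver and blood toxicity after Week 24 goes uncompared between arms.** The by-visit tables, ANCOVA, AE tests and discontinuation summaries all address it.
- **That the worst-value table biases the comparison.** Earlier values precede randomisation, so they add noise and not bias. A whole-treatment table also serves ARM-1 and general MTX safety.
- **That a formal test on that table would be underpowered.** SAP 7.2 does not say the Wilcoxon test applies to it.

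**Conclusion.** The point holds as a minor gap in the analysis plan. SAP 7.2 and Protocol 9.2.3.2 grade laboratory values only as Low, Normal or High, and their single worst-value table spans the shared MTX period from Week 0. Read with the rest of the plan, readers can usually infer that a few marked cases exist and often which arm they fall in. They cannot read how many subjects per arm crossed a clinical threshold after the dose changed. Under the stated assumptions, the planned worst-value table shows a difference of about 3 points where a threshold count after Week 24 shows 7, with most of the gain from the threshold. The absence of the count follows from the text; its size rests on assumed rates, since the documents give no background or event rate. No primary conclusion is affected.

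**What to change.** In SAP 7.2, add for ARM-2 and ARM-3:

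- The worst AST and ALT after Week 24, up to Week 48 or early termination, as multiples of the site's ULN: ≤1, >1–2, >2–3, >3–5, >5.
- The worst WBC, neutrophil and platelet values over the same window, by one named toxicity scale, with the grade that counts as cytopenia fixed before database lock.
- Both as shifts from Week 24, with a country-stratified ARM-2 v ARM-3 risk difference and 95% CI for >3 x ULN and for graded cytopenia, labelled descriptive.

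Keep the existing L/N/H tables, ANCOVA and AE tests.

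The cost is SAP wording and a few tables. The tests are already collected (Protocol 7.4; the differential count gives neutrophils), and the L/N/H tables already need the site reference limits. The downsides are sparse top categories, wide intervals, and only two scheduled laboratory visits after randomisation, so a rise between visits is missed here although it may appear as an AE. The gain is a count that can be interpreted, not power.
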